8.5 ADVERSE EVENTS FOLLOW-UP

It is the Investigator’s responsibility to maintain documentation of each reported adverse event. All adverse events will be followed in accordance with applicable licensing requirements. Such documentation will include the following:

- Adverse Event (Diagnosis not symptom)
- Detailed drawings or photographs, when appropriate
- Date and time of onset
- Date and time of resolution
- Adverse event intensity and classification, as applicable
- Treatment regimen instituted, including concomitant medications prescribed, in accordance with applicable licensing requirements
- Any referral to another health care provider if needed
- Outcome, ocular damage (if any)
- Likely etiology.
- Best corrected visual acuity at the discovery of the event and upon conclusion of the event

In addition, if an infiltrate(s) is present, the Investigator will complete the Corneal Infiltrate Assessment Form / eCRF.

Photographs or video recordings may be collected at the Investigator’s discretion for purposes of documenting adverse event findings.

Visual acuity (best corrected) should be recorded prior to the report of an adverse event (as part of the Baseline Evaluation), upon the subject’s report of the adverse event, and after the adverse event has resolved.

Subjects who present with an adverse events should be followed by the Investigator, within licensure, until all signs and symptoms have returned to pre-treatment status, stabilized, or been satisfactorily resolved. If further treatment (i.e. beyond licensure) is required, the patient will be referred to the appropriate health care provider. The Investigator should use his/her clinical judgment as to whether or not a subject (eye) reporting with an adverse event should continue in the study. If a subject is discontinued from the study, it will be the responsibility of the Investigator to record the reason for discontinuation. The investigator will also complete the Adverse Event Classification (AEC) Outcome form / eCRF. Any subjects with ongoing adverse events related to the test article as of the final study visit date should be followed to resolution of the adverse event or until referral to an appropriate health care provider, as recommended by the Investigator.

9.1 STATISTICAL METHODS TO BE EMPLOYED

All data summaries and statistical analyses will be performed using either the SAS software Version 9.4 or higher (SAS Institute, Cary, NC) or SPSS software Version 23.0 or higher (IBM Corp, Armonk, NY).

Description of Summary Tables

Summary tables (Descriptive statistics and/or frequency tables) will be provided for all baseline, efficacy and safety variables for each subject/eye as appropriate. Continuous variables will be summarized with descriptive statistics (n, mean, standard deviation (SD), median, minimum and maximum). Frequency count and percentage of subjects or eyes within each category will be provided for categorical variables.

Summaries will be presented by study lens type and will be performed separately by study population defined in section 9.7. Efficacy variables will be summarized descriptively on both the analysis and safety population. Safety variables will be summarized descriptively for the safety population. Unscheduled visits will be summarized separately if applicable. If the difference between the analysis and safety population is higher than 15%, a sensitivity analysis will be conducted on the safety population.

Data summarization will be performed by OTG-i, with oversight by the JJVCI study responsible biostatistician.

Raw data will be provided to OTG-i by JJVCI/Bioclinica in the Study Data Tabulation Model (SDTM) format in conformance to Clinical Data Interchange Standards Consortium (CDISC) standards. OTG-i will be responsible to create CDISC Analysis Data Model (ADaM) datasets as well as the display outputs including tables, listings and figures (TLFs) based on the CDISC ADaM datasets. For more details about CDISC, SDTM and ADaM, please refer to www.cdisc.org.

OTG-i shall follow specifications of ADaM datasets and mock shells of TLFs provided by JJVCI. Sample datasets, ADaM specifications, and mock shells of TLFs may be provided to OTG-i by JJVCI midway through the study if needed.

Description of Analysis Methods

Efficacy Analysis Set

The primary and secondary analysis will be performed on all randomized subjects who successfully completed the study without any protocol deviations that the study responsible clinician documents as impacting the assessment of the hypotheses (i.e. analysis population). Justification of excluding subjects with protocol deviations in the analysis population set will be documented.

Analysis Methods

The binocular central distance high contrast, high illumination (250 cd/m²) TCVA, the binocular central distance high contrast, low illumination (2.5 cd/m²) TCVA and the binocular central intermediate vision high contrast, medium illumination (50 cd/m²) TCVA will be analyzed together using a linear mixed model. The model will include the experimental design factors: sequence of lens wear, period, lens type, condition (determined jointly by distance, illumination and eccentricity) as well as lens type by condition interaction as fixed effects; and subject as a random effect. Other baseline characteristics known of importance such as age, gender and race may be included as fixed covariates when appropriate. The covariance between residual errors from the same subject and period at different conditions will be selected based on the finite-sample corrected Akaike's Information Criterion (Keselman et al., 1998). Covariance structures considered may include:

- Variance Component (VC)
- Homogenous Compound Symmetry (CS),
- Heterogeneous Compound Symmetry (CSH),
- Heterogeneous Variance Component (UN(1))
- Unstructured Covariance Structure (UN).

For UN(1) covariance structures, condition nested within subject and period will be included as an additional random effect. For the remaining structures only subject will be included as a random effect. The improved Kenward and Roger method (Kenward and Roger, 2009) using the KENWARDROGER2 option will be used for the calculation of the denominator degrees of freedom. Heterogeneous models between the study lenses may be considered when appropriate. The log-likelihood ratio test will be used to test for homogeneity of variances between lens types.

Primary Hypothesis Testing:

The null and alternative hypotheses for non-inferiority in the binocular central distance high contrast high illumination TCVA are as follows: $H_0: \mu_1 - \mu_2 \leq -0.5$ v.s. $H_a: \mu_1 - \mu_2 > -0.5$, where μ_1 and μ_2 are the population mean of binocular central distance high contrast high illumination TCVA for the Test lens and the Control lens, respectively. Comparisons between the Test lens and Control lens will be conducted using two-sided 95% confidence intervals constructed for least-square means (LSM) difference (Test - Control) at central distance high contrast high illumination. Non-inferiority will be concluded if the lower limit of the LSM difference is greater than -0.5 VA units.

Secondary Hypothesis Testing:

The null and alternative hypotheses for non-inferiority in each of the secondary endpoints are as follows: $H_0: \mu_1 - \mu_2 \leq -0.75$ v.s. $H_a: \mu_1 - \mu_2 > -0.75$, where μ_1 and μ_2 are the population mean of the corresponding endpoint for the Test lens and the Control lens, respectively. Comparisons between the Test lens and Control lens will be conducted using two-sided 95% confidence intervals constructed for least-square means (LSM) difference (Test - Control) at central distance high contrast low illumination and central intermediate vision high contrast medium illumination, respectively. Non-inferiority will be concluded if the lower limit of the LSM difference is greater than -0.75 VA units.

Bayesian analysis may be considered if the data is not normally distributed.

Further exploratory analysis can be undertaken if necessary at the discretion of the study responsible clinician.

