22.	Familiarization with visual performance assessment tasks	The subject will undergo familiarization with the study visual performance assessment tasks (time controlled visual acuity, detection tests, driving simulation and computer based reaction time game).	Manual of Procedures
23.	Lens Removal	The contact lenses are removed and discarded.	
24.	Biomicroscopy	Biomicroscopy will be performed OD and OS. Standard Slit Lamp Classification Scales will be used to grade the findings. For the limbal and conjunctival redness, 0.5 unit increments will be used in the grading.	Manual of Procedures [REDACTED]
25.	Distance Spherocylindrical Refraction and Exit Visual Acuity	An optimal, binocular balanced distance spherocylindrical refraction will be performed. The distance visual acuity to the nearest letter will be recorded OD, OS and OU.	Manual of Procedures [REDACTED]
26.	Continuance	Indicate whether the subject will continue to the next visit. If not, proceed to Final Evaluation.	
27.	Lens Order	Custom Test and Control lenses will be ordered. Visit 2 will be scheduled once the study lenses are received.	

Visit 2: First Measurement Visit (2 to 6 weeks after Visit 1)			
Step	Descriptor	Details	Appendix
1.	Concomitant Medications/Treatments	Questions regarding the subjects' medications and/or treatments.	
2.	Subject Reported Ocular Symptoms	Record any symptoms or problems that the subject may experience with their habitual contact lenses, if applicable. Subject will not be asked about specific categories of complaints, but the severity or frequency will be recorded in the following categories: 
 Burning/Stinging Itchiness/Scratchiness 	[REDACTED]

		
 • Dryness • Lens Awareness • Grittiness/Foreign Body Sensation • Redness • Irritation/Discomfort • Cloudy/Blurry/Hazy • Variable Vision • Other 	
3.	Distance Spherocylindrical Refraction and Entrance Visual Acuity	An optimal, binocular balanced distance spherocylindrical refraction will be performed. The distance visual acuity to the nearest letter will be recorded OD, OS and OU.	Manual of Procedures [REDACTED]
4.	Biomicroscopy	Biomicroscopy will be performed OD and OS. Standard Slit Lamp Classification Scales will be used to grade the findings. For the limbal and conjunctival redness, 0.5 unit increments will be used in the grading.	Manual of Procedures [REDACTED]
5.	Continuance	Indicate whether the visit needs to be rescheduled.	

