9.7 EVALUABLE SUBJECTS

Accountability (disposition) of all enrolled subjects will be presented in each of the following status subgroups.

1. Completed: Randomized subjects who are eligible to participate in the study and have successfully completed all required visits including the final visit.
2. Discontinued: Randomized subjects who are prematurely discontinued from the study due to (i) lost to follow-up, (ii) withdrawal of consent, (iii) death, (iv) unsuccessful dispensing (lack of efficacy or safety), (v) safety reasons at the discretion of the investigator, (vi) dissatisfactory of eligibility criteria (e.g., pregnancy), (vii) noncompliance of the study lens wear schedule.

3. Total Dispensed: Randomized subjects who administered the test article at least once (i.e. lens insertion occurred in at least one eye).
4. Enrolled Not Dispensed: Subjects who were (i) enrolled in the study (provided informed consent) but failed to satisfy the eligibility criteria (inclusion/exclusion criteria), (ii) randomized but discontinued or drop out prior to administering the test article, or (iii) not randomized to treatment for any reason.
5. Total enrolled (i.e. completed + discontinued + Enrolled not dispensed).

Subjects will be allocated to the following study populations. Safety variables will be summarized on the safety population whereas efficacy variables will be summarized on both the analysis and safety population.

1. Safety Population: All subjects who are administered the test article and have at least one observation on any safety or/and efficacy variables.
2. Analysis Population: All subjects who have successfully completed all required visits without any protocol deviations that the study responsible clinician documents as impacting the assessment of the hypotheses.

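### Section 9.1 gives all three vision conditions one shared period effect; adding period by condition would remove a small, avoidable error in each lens comparison

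*Combined protocol and SAP*

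**What the plan says.** Under Analysis Methods in section 9.1, the three binocular central TCVA endpoints (distance at 250 cd/m², distance at 2.5 cd/m², intermediate at 50 cd/m²) "will be analyzed together using a linear mixed model". On the fixed effects, the section starts from the crossover design: "The model will include the experimental design factors: sequence of lens wear, period, lens type, condition". The list then closes with one interaction and the random term: "as well as lens type by condition interaction as fixed effects; and subject as a random effect". Lens type by condition is the only interaction.

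The same section allows some flexibility. Baseline covariates such as age may be added. On the residual structure: "The covariance between residual errors from the same subject and period at different conditions will be selected", the choice being made by corrected AIC from VC, CS, CSH, UN(1) and UN, and variances may differ between lenses. None of these lets the period effect vary by condition.

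Non-inferiority is judged separately at each condition from a two-sided 95% interval, with a margin of -0.5 VA units for the primary endpoint and -0.75 for the two secondary ones.

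Three design features bear on the point:
- **Practice.** At Visit 1, step 22 of section 4.7.1: "The subject will undergo familiarization with the study visual performance assessment tasks". Visit 2 comes 2 to 6 weeks after that, and Visit 3 comes 2 to 14 days after Visit 2.
- **Randomisation.** Section 4.5 uses permuted blocks of two and randomises at the start of Visit 2. Each subject's order of test conditions is the same for both lenses.
- **Analysis set.** Section 9.7 keeps only subjects who finish every required visit and have no deviation that the responsible clinician records as affecting the hypothesis tests. Section 9.2 targets at least 20 completers and at most 25 enrolled.

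**The concern.** By including period, the plan accepts that results may shift between visits. By including lens type by condition, it accepts that the conditions may behave differently. It does not allow the visit shift itself to differ by condition. Three separate 2x2 crossover analyses would each have their own period term; the joint model drops this without a stated reason.

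A condition-specific shift is plausible. TCVA is a timed task that needs familiarisation, and the conditions differ in luminance and in distance (4 m or 67 cm). Practice may help one more than another. Repeating the test order at the second visit does not remove such an effect.

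Two things would be at stake. The unmodelled part of the shift goes into the residual and widens the interval. And if the sequences are unequal in the analysis set, part of the shift is credited to, or charged against, the Test lens at that condition.

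**Working it through.** The plan gives no power calculation, SD or learning size, so there is no figure of its own to reproduce.

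**Bias.** Let τ be the true Test minus Control difference at one condition, π that condition's shift from Visit 2 to Visit 3, and π̄ the average shift over the three conditions. Subjects on Test/Control have an expected within-subject difference of τ - π; those on Control/Test, τ + π. Averaged over all subjects this is τ + [(n_CT - n_TC)/N] × π. Under VC or CS with complete data, the planned model subtracts the same multiple of π̄. What remains is

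bias = [(n_CT - n_TC)/N] × (π - π̄).

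For N = 20, size of the bias in VA units (sign depends on which sequence is larger):

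| Split | Multiplier | Departure 0.1 | Departure 0.2 | Departure 0.4 | Last column ÷ 0.5 |
|---|---|---|---|---|---|
| 10/10 | 0 | 0 | 0 | 0 | 0% |
| 11/9 | 0.1 | 0.01 | 0.02 | 0.04 | 8% |
| 12/8 | 0.2 | 0.02 | 0.04 | 0.08 | 16% |
| 13/7 | 0.3 | 0.03 | 0.06 | 0.12 | 24% |

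The departure π - π̄ is assumed. A departure of 0.4 needs, for example, a gain of 0.6 at one condition and none at the other two: 0.6 - 0.2 = 0.4. Generalised least squares on the full design confirms the formula under VC and CS. Under CSH or UN the conditions are weighted differently. At 13 Test/Control and 7 Control/Test, with shifts of 0, 0.4 and 0.2, the biases are +0.06, -0.06 and 0 under VC or CS, but +0.024, -0.096 and -0.036 under one unequal UN matrix. With period by condition added, the bias is 0 at every split and structure tried.

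**How likely are the splits?** Assume 20 are analysed and losses are unrelated to sequence.
- 22 randomised (11/11), 2 lost: 11/9 is the worst possible.
- 24 randomised (12/12), 4 lost: 12/8 either way has probability 2 × C(12,4)/C(24,4) = 990/10,626 = 9%.
- 25 randomised (13/12), 5 lost: 12/8 or worse has probability (792 + 6,435 + 1,287)/53,130 = 16%. The 792 is 13/7, or 1.5%.

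**Standard error at 10/10 (no bias).** Under VC, each of the 120 observations carries an unmodelled ±(π - π̄)/2. With a gain of 0.6 at one condition the departures are 0.4, -0.2 and -0.2, so the added sum of squares is 40 × (0.04 + 0.01 + 0.01) = 2.4. Residual degrees of freedom are 120 - 20 (subjects) - 3 (lens and lens by condition) - 2 (condition) - 1 (period) = 94, so the residual variance rises by 2.4/94 = 0.0255.
- Assumed residual SD 0.35: √[(0.1225 + 0.0255)/0.1225] = 1.10, or 10% too wide. Simulation gave 0.121 against 0.110.
- Assumed residual SD 0.27: √[(0.0729 + 0.0255)/0.0729] = 1.16, or 16%. A gain of 0.3 adds a quarter as much variance, giving 4%.
- SD 0.4, within-visit correlation 0.3, covariance chosen by corrected AIC: 0.127 against 0.124 for departures up to 0.2 (2%), and 0.138 against 0.125 for departures up to 0.4 (10%). The empirical SE was the same with and without the term.

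**Error rate with the true difference at the primary margin (nominal 2.5%).** With the split fixed at 7/13 and a departure of 0.4, false non-inferiority was 9.6% under the planned model and 2.8% with the term (250 runs; Monte Carlo error 1 to 2 points). Averaged over random splits, with a gain of 0.6 and SD 0.35, the planned model gave about 1.3% to 2.6%.

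**The case against.** The strongest reply is that the design already limits the problem. Blocks of two cap the imbalance at one subject at randomisation. Because randomisation waits until Visit 2, failures in screening, fitting or lens ordering cannot unbalance the sequences. The cap of 25 counts enrolled subjects, so fewer may be randomised. Familiarisation should reduce learning, and nothing in the documents supports a gain as large as 0.6 VA units at one condition alone. Sections 4.1 and 9.2 call the hypotheses exploratory, and 9.1 allows further exploratory analysis. All of this stands, and it limits the size of the point.

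It does not remove the gap. Losses and exclusions after randomisation can still unbalance the analysis set, and section 4.10 does not say that a replacement takes the lost subject's sequence. Choosing the covariance by corrected AIC cannot repair an omission in the mean model. Nor can the safety-population sensitivity analysis, which changes the subjects analysed but not the specified model.

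A reader might infer that the planned model generally inflates false non-inferiority, or that a bias of 16% of the margin is to be expected. The documents support neither. The 16% needs both a 12/8 split and a 0.4 departure at the primary condition. If the excess learning of 0.6 were at a secondary condition, the comparison is 0.08/0.75 = 11%, and the primary departure would be 0.2, giving 0.04 at 12/8. Over random splits the error rate stays close to or below 2.5%, because the wider interval offsets the split-dependent shift.

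**Conclusion.** The gap is real but small. Section 9.1 adjusts each condition's lens difference for a period effect pooled over three conditions, and nothing it permits relaxes that. If learning differs by condition, the usual effect is a model standard error roughly 2% to 16% too wide, which makes non-inferiority harder to conclude, not easier. Bias needs unequal sequences as well. At the most likely splits it is 0 to 0.04 VA units for departures of 0.1 to 0.4, at most 8% of the primary margin; 0.08 and 0.12 are tail cases. With no condition-specific learning there is neither bias nor inflation. These sizes rest on assumed SDs, correlation, learning gains and loss unrelated to sequence; the closed form for bias also assumes VC or CS with complete data. This is a cheap improvement of low severity for an exploratory pilot.

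**What to change.** In section 9.1, add period by condition to the list of fixed effects, so that each condition's lens difference is adjusted for its own period effect. Sequence by condition may be added for symmetry but is not needed to remove the bias. Leave the rest of the model as planned.

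The cost is one line of text, no new data and 2 degrees of freedom. With known covariance there is no loss of precision at 10/10. At 13/7 the SE rises about 3% (0.1607 to 0.1657 for one condition under VC). The term should be specified before the data are seen; under section 9.6, adding it later would be a change from plan that has to be documented and justified in the study report.

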9.2 NUMBER OF SUBJECTS BY SITE AND JUSTIFICATION FOR SAMPLE SIZE

A minimum of 20 subjects are targeted to complete the study as the cohort population. Subjects who are found to be ineligible, or who are discontinued or incomplete, will be classified as the non-cohort population. The total number of subjects enrolled may not exceed 25 subjects, except by joint agreement of the Investigator and Sponsor. Since this is a pilot study and all the hypotheses are exploratory in nature, the sample size was selected by the study responsible clinician and was not based on any empirical power calculation.

9.3 LEVEL OF STATISTICAL SIGNIFICANCE

All planned analysis for this study will be conducted with an overall type I error rate of 5%. Since this study is exploratory in nature, no adjustment for multiple comparisons will be conducted.

9.4 CRITERIA FOR STUDY TERMINATION

In addition to the stopping rules defined in section 9.1, the occurrence of one or more Serious Unanticipated Adverse Device Effect (USADE), or any SAE where the relationship to study agent cannot be ruled out, may result in stopping further dispensing of investigational product. In the event of a USADE or SAE, the Sponsor may unmask the treatment regimen for the subject(s) and may discuss this with the Investigator before any further subjects are enrolled.

The sponsor may determine when a study will be stopped. The principal investigator always has the discretion to initiate stopping the study based on subject safety or if information indicates the study's results may be compromised.

9.5 PROCEDURE FOR ACCOUNTING FOR MISSING, UNUSED, AND SPURIOUS DATA

Missing or spurious values will not be imputed. The count of missing values will be included in the summary tables and listings.

9.6 PROCEDURE FOR REPORTING DEVIATIONS FROM STATISTICAL PLAN

The analysis will be conducted according to section 9.1. There are no known reasons for which it is planned to deviate from these analysis methods. If for any reason a change is made, the change will be documented in the study report along with a justification for the change.

9.7 EVALUABLE SUBJECTS

Accountability (disposition) of all enrolled subjects will be presented in each of the following status subgroups.

1. Completed: Randomized subjects who are eligible to participate in the study and have successfully completed all required visits including the final visit.
2. Discontinued: Randomized subjects who are prematurely discontinued from the study due to (i) lost to follow-up, (ii) withdrawal of consent, (iii) death, (iv) unsuccessful dispensing (lack of efficacy or safety), (v) safety reasons at the discretion of the investigator, (vi) dissatisfactory of eligibility criteria (e.g., pregnancy), (vii) noncompliance of the study lens wear schedule.

3. Total Dispensed: Randomized subjects who administered the test article at least once (i.e. lens insertion occurred in at least one eye).
4. Enrolled Not Dispensed: Subjects who were (i) enrolled in the study (provided informed consent) but failed to satisfy the eligibility criteria (inclusion/exclusion criteria), (ii) randomized but discontinued or drop out prior to administering the test article, or (iii) not randomized to treatment for any reason.
5. Total enrolled (i.e. completed + discontinued + Enrolled not dispensed).

Subjects will be allocated to the following study populations. Safety variables will be summarized on the safety population whereas efficacy variables will be summarized on both the analysis and safety population.

1. Safety Population: All subjects who are administered the test article and have at least one observation on any safety or/and efficacy variables.
2. Analysis Population: All subjects who have successfully completed all required visits without any protocol deviations that the study responsible clinician documents as impacting the assessment of the hypotheses.

